Prior to Day 28 in Parts 1 and 2, subjects must be withdrawn from study treatment if a second-line treatment for acute GvHD is introduced. Second-line treatment may be introduced per investigator discretion prior to Day 28 if a subject experiences disease progression and/or new organ involvement or no change in acute GvHD status after at least 7 days of study treatment (Day 6). Subjects who experience recurrent malignancy will also be withdrawn from study treatment (Section 12.11).

An increase in steroid dose following steroid taper does not constitute second-line treatment; however, steroid treatment at methylprednisolone doses (or equivalent) of greater than 2 mg/kg/day for GvHD treatment will be considered a treatment failure.

Subjects classified as treatment failures will be included in the analysis, but will not be counted as either CR or PR for the primary (overall response) or key secondary (GI response) endpoints. Subjects classified as treatment failures will not be replaced.

All subjects will be followed up at Days 100, 180 and 365.

Data Monitoring Committee

A Data Monitoring Committee (DMC) will independently evaluate safety and efficacy data (Section 15.4). The recommendations of the DMC will be based on the analysis of safety in Parts 1 and 2 and the interim analysis of Part 2 (Section 8.2.2).

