8.4 Outcome Measures

8.4.1 Primary Outcome Measure (Parts 1 and 2)

The primary outcome measure for Parts 1 and 2 is the proportion of subjects achieving overall response at Day 28. The overall response is defined as GvHD CR + PR, as defined below:

- GvHD CR is complete resolution of all signs and symptoms of acute GvHD in all organs without intervening salvage
- GvHD PR is improvement of 1 stage in 1 or more organs involved in GvHD without progression in other organs

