8.4.2 Secondary Outcome Measures

8.4.2.1 Efficacy (Parts 1 and 2)

Key Secondary Efficacy Outcome Measures

1. Proportion of subjects achieving GI response at Day 28. Gastrointestinal response is defined as GI CR + PR, which are defined as follows:
 - GI CR is defined as
 - a) Able to eat; not requiring parenteral nutrition, and
 - b) Passing primarily formed stools
 - GI PR is defined as
 - a) Decrease in need for parenteral nutrition to $\leq 50\%$ of required calories; and
 - b) Reduction of stool volume by $\geq 50\%$, without ileus

Other Secondary Efficacy Outcome Measures

1. Proportion of subjects achieving overall response at Day 56
2. Change from baseline in acute GvHD grading at Days 28, 56 and 180
3. Incidence of chronic GvHD at Days 100, 180 and 365

4. Duration of any overall response
5. Duration of any GI response
6. Overall survival through Days 100, 180 and 365
7. Transplant-related mortality at Days 28, 56, 100 and 180
8. Failure-free survival at Days 100 and 180
9. GvHD-free survival at Days 28, 56, 100 and 180
10. Infection-related mortality at Days 28, 56, 100 and 180
11. GvHD-related mortality at Days 28, 56, 100 and 180
12. All-cause mortality at Days 28, 56, 100 and 180

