9.3 Withdrawal from Study Participation and Discontinuation of Study Treatment

Any subject may voluntarily withdraw at any time consent for continued participation in the study and data collection. Every effort should be made prior to enrollment to ensure subjects are willing to comply with study procedures and assessments. The reason for withdrawal will be recorded on the End of Study CRF. Additionally, the investigator and sponsor have the discretion to discontinue any subject from the study if, in their judgment, continued participation would pose an unacceptable risk for the subject. Assessments to be performed at the termination visit (including in cases of withdraw or discontinuation) are described in Section 10.6 and Section 20.2.

Whenever possible, all subjects who prematurely withdraw from the study will be followed through Day 28 or 2 weeks after the last dose of study treatment, whichever comes later (refer to Section 10.6 for additional details), unless otherwise indicated below.

Subjects will be discontinued from study treatment for the following reasons:

- The subject has a lower GI biopsy within 7 days of informed consent that in the opinion of a pathologist is inconsistent with acute GvHD (Section 11.3). If the results are obtained prior to the first dose of study treatment, the subject will be withdrawn from the study prior to study treatment for Part 1 and without being randomized for Part 2.
- The subject becomes pregnant.
- The subject starts a second-line treatment for acute GvHD prior to Day 28 (Section 8.2).
- The subject experiences recurrent malignancy (Section 12.11).
- If the Sponsor medical monitor or the investigator deem it is in the best interest of the subject

Subjects who discontinue study treatment and/or the study will not be replaced.

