Subjects who discontinue study treatment after Day 28 will complete the study completion/termination visit as an office visit 2 weeks (± 1 day) after the last dose of study treatment. Subjects who withdraw from the study after Day 56 will be encouraged to complete the study completion/termination visit at the time of discontinuation. In the event that it is not feasible for the subject to visit the site at the study completion/termination visit after Day 56, the visit may be conducted with a phone call.

Subjects who discontinue study treatment will not attend any other subsequent visits other than Day 28 and the study completion/termination visit (if applicable), except as needed for follow-up of recovering/resolving AEs (see Section 12.1.2).

In the event of subject discontinuation due to an AE, clinical and/or laboratory investigations that are beyond the scope of the required study observations/assessments may be performed as part of the evaluation of the event. These investigations will take place under the direction of the investigator in consultation with the sponsor, and the details of the outcome may be reported to the appropriate regulatory authorities by the sponsor.

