7.2.2 Other Secondary Efficacy Outcome Measures

Proportion of subjects achieving GvHD overall response at Day 56

GvHD overall response at Day 56 will be based on all the investigators' assessments or the adjudicated data of GvHD response obtained at Day 56 (with a +1 day window) in the efficacy analysis set and using the NRI approach as for the primary outcome measure in Section 7.1.

Change from baseline in acute GvHD grading at Days 28, 56 and 180

Staging of GvHD will be performed by the investigator according to the modified IBMTR grading system, and recorded on CRF STAGE module. The degree of involvement of skin, GI and liver is classified by stage on a scale of 0 to 4 and the grade of acute GvHD is classified on a scale of A to D.

Shift tables from baseline to Days 28, 56 and 180 visits will be provided for acute GvHD grading and organ system (involvement of skin, GI and liver) staging separately in the efficacy analysis set.

Incidence of chronic GvHD at Days 100, 180 and 365

At baseline and Days 100, 180 and 365, the investigator will assess the subject for chronic GvHD and acute/chronic GvHD overlap syndrome. The number and percentage of subjects who have clinical evidence of chronic GvHD will be summarized at baseline and Days 100, 180 and 365 by organ systems (skin involvement, dry mouth/mouth sores/ulcers, dry eyes, joint involvement, liver involvement with cholestasis, esophageal involvement, obstructive lung disease) in the SAF.

Duration of any overall response

Duration of overall response is defined as the time from the date of first overall response (GvHD CR or PR) until the first date of progression (GvHD progressive disease [PD] on CRF INVRES module) or death in the absence of progression. Subjects without progression or death will be censored at the date of last GvHD response assessment.

Only subjects with an overall response will be summarized for duration of overall response. Descriptive data, including 25th percentile, median and 75th percentile will be estimated using Kaplan-Meier method. The summaries will be produced separately for investigator assessment and adjudicated data. Duration of overall response will also be presented using corresponding Kaplan-Meier plots.

Duration of any GI response

Duration of GI response will be derived and summarized for subjects who achieved a GI response using the same approach as described for the duration of overall response above, based on GI response assessments.

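### Partial response and GI response carry no salvage condition, and the treatment-failure rule stops at the Day 28 endpoints, so improvement after later second-line therapy can count in the Day 56, later GI and duration endpoints

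*Protocol*

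**What the plan says.** **Response definitions.** Overall response is CR plus PR (Protocol 8.4.1, repeated in SAP 7.1). For CR: "GvHD CR is complete resolution of all signs and symptoms of acute GvHD in all organs without intervening salvage". For PR: "GvHD PR is improvement of 1 stage in 1 or more organs involved in GvHD without progression in other organs". GI CR and GI PR (Protocol 8.4.2.1, SAP 7.2.1) rest on nutrition and stool alone and do not mention salvage.

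**Treatment failures.** Protocol 8.2 keeps these subjects in the analysis, but they "will not be counted as either CR or PR for the primary (overall response) or key secondary (GI response) endpoints". Both named endpoints are at Day 28. The list of other secondary endpoints includes "Proportion of subjects achieving overall response at Day 56", and Section 8.4.3 adds GI CR and PR at Days 28, 56 and 180 by baseline grade. The failure rule is not extended to the later time points.

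**Second-line therapy.** Before Day 28, "subjects must be withdrawn from study treatment if a second-line treatment for acute GvHD is introduced" (Protocol 8.2). Section 9.3 lists as a reason for stopping study treatment: "The subject starts a second-line treatment for acute GvHD prior to Day 28". Section 10.4 instead bars other GvHD treatment throughout the study and takes users off study treatment. The only exemption it describes is for starts before Day 28 that meet the stated criteria. Section 10.6 restricts later visits: "Subjects who discontinue study treatment will not attend any other subsequent visits other than Day 28 and the study completion/termination visit (if applicable". Follow-up of unresolved adverse events is the only exception.

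**Missing responses.** In Part 1 a missing response is non-response at Day 28 and at other time points, including Day 56 (Protocol 13.3, SAP 5.1). In Part 2, Section 13.3 states the rule for the primary endpoint only. Section 13.4.2 says that Day 56 response is analysed in a similar way to Day 28.

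**Duration.** SAP 7.2.2 runs a response from the first CR or PR to progression or death: "Subjects without progression or death will be censored at the date of last GvHD response assessment".

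**The concern.** A subject whose disease resolves after salvage fails CR but can still satisfy the PR wording, and so counts as an overall responder wherever the failure rule does not reach. Non-responder imputation does not help, because it deals with missing assessments and not with an observed improvement after salvage. Later response rates and durations would then mix the effect of the study drug with that of second-line therapy.

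The plan already treats salvage as failure in three places: the CR definition, the Day 28 failure rule, and failure-free survival (Protocol 11.12), where second-line treatment counts as failure with no Day 28 limit. The later response endpoints lack the same logic.

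In Part 2 the between-group comparison at Day 56 is at stake. In Part 1, which has no control, salvage responses would inflate the Day 56 GI response and duration data. Protocol 8.2.2 lists both among the inputs to the decision on Part 2.

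**Working it through.** **1. The plan's own figures.** No figure is stated for Day 56. The stated 67 per group is for Day 28 response at 40% versus 65%, 1-sided 0.025, 80% power (Protocol 13.1). On the log odds ratio scale:

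- ln OR = ln[(0.65/0.35)/(0.40/0.60)] = 1.0245
- n = 7.849 × [1/(0.40 × 0.60) + 1/(0.65 × 0.35)] / 1.0245² = 64.03
- Inflation for one nonbinding beta-spending look at 50% (gamma −2) is 1.0330, so 64.03 × 1.0330 = 66.1, which rounds up to 67.

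The interim beta spend of 0.0538 and the futility p-value of 0.3430 (Protocol 13.5) also reproduce. None of these depends on how Day 56 response is defined.

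**2. Which subjects can reach a Day 56 response after salvage.**

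| Start of second-line therapy | What the text does with the subject | Post-salvage PR at Day 56? |
|---|---|---|
| Before Day 28 | Off study treatment (8.2, 9.3), so no Day 56 visit (10.6). A separate termination visit uses the Day 365 assessments, which include no response assessment (Table 1). | No. Missing counts as non-response in Part 1; handling in Part 2 is not stated. |
| Days 28 to 49 | 8.2 and 9.3 limit their second-line rule to before Day 28; 10.4 takes users off study treatment. | Only if 8.2/9.3 prevail. Otherwise Day 56 is missing, as in the row above. |
| After the Day 49 dose, before Day 56 | No study treatment is left to stop. Care is at the investigator's discretion (8.2) and the Day 56 visit includes a response assessment (Table 1). | Yes |

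Subjects who complete dosing also have response assessments at Days 100 and 180 under standard of care, so the Day 180 GI response and the durations are open to salvage for longer. Section 8.2 also says that all subjects are followed at Days 100, 180 and 365, which does not fit easily with Section 10.6. Day 56 is not in that list, so the table is unchanged.

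**3. Duration.** Under SAP 7.2.2 only progression or death ends a response. Second-line therapy started without recorded progression leaves the response running. A first response reached after salvage is not excluded. One example is a PR at the Day 28 visit in a subject who began second-line therapy earlier: the failure rule removes it from the Day 28 endpoints but not from the duration of any response.

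**4. Size in Part 2.** Assumptions, since the documents give no Day 56 rates and no salvage rates: Day 56 rates without salvage equal the Day 28 planning rates (40% and 65%), and a fraction q of non-responders in each arm becomes a post-salvage PR.

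- Control: 40 + 60q. GLASSIA: 65 + 35q. Difference: 25 − 25q = 25 × (1 − q).

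| q | Control % | GLASSIA % | Difference (points) |
|---|---|---|---|
| 0 | 40.0 | 65.0 | 25.00 |
| 0.05 | 43.0 | 66.75 | 23.75 |
| 0.10 | 46.0 | 68.5 | 22.50 |

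With unequal fractions the difference is 25 − (60q_control − 35q_GLASSIA). It shrinks whenever q_GLASSIA is less than 60/35 = 1.71 times q_control, which covers equal fractions and any excess of salvage on control.

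**5. Size in Part 1.** With 20 evaluable subjects and complete Day 56 data, each post-salvage GI responder adds 1/20 = 5 percentage points to the Day 56 GI response rate.

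**The case against.** The strongest objection is that most of the apparent route is closed. A reader might infer that a Day 28 non-responder who starts second-line therapy on Day 30 plainly stays on schedule and can score a PR at Day 56. The documents do not support that as a plain reading. Section 10.4 would take the subject off study treatment, Section 8.2 itself ends study treatment at treatment failure without a Day 28 limit, and Section 10.6 would then leave no Day 56 response visit. This stands: the clear window is about seven days, and Days 28 to 49 rest on an unresolved conflict.

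A reader might also infer that the 25-point difference shrinks to 20. That needs q = 0.20, for example half of all Day 28 non-responders starting second-line therapy by Day 56 and 40% of those improving (0.5 × 0.4). Neither rate is in the documents, and the pool includes deaths, withdrawals and subjects who started before Day 28. If starts were uniform over Days 28 to 56 and only Days 49 to 56 counted, the same inputs give q = 0.20 × 7/28 = 0.05, or 23.75 points.

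Other points carry weight. A responder who needs second-line therapy will often have progressed, which already ends the response. The adjudication charter, which is not public, may contain a salvage rule. The Part 2 threshold is Day 28 overall response, the analysis is run when the last Part 1 subject reaches Day 28, and Section 8.2.2 attaches Day 56 to GI response rather than overall response. Finally, the SAP covers Part 1 only, one subject was enrolled, and only listings are produced.

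These limit the size of the problem. They do not supply the missing rule: neither document says how second-line therapy after Day 28 counts for the later response and duration endpoints.

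**Conclusion.** The gap is real and modest. GvHD PR and both GI response definitions lack the salvage condition that CR has, and the failure rule stops at the Day 28 endpoints. Improvement after second-line therapy can therefore count at Day 56 (clearly for starts after Day 49, conditionally for Days 28 to 49), in GI response at Days 56 and 180, and in both duration endpoints. For starts before Day 28, Day 56 response is unaffected in Part 1; Part 2 does not state what happens to the missing value.

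On the equal-q assumption an assumed 25-point Day 56 difference falls to 23.75 at q = 0.05 and 22.5 at q = 0.10, a bias toward no difference. In Part 1 the bias is upward, in supporting data for the Part 2 decision and not in its 55% threshold.

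A reader might infer from the PR wording that the primary endpoint is exposed. It is not: the treatment-failure rule protects both Day 28 endpoints, and the sample size and type I error do not change. Because the trial stopped after one subject, the point concerns the design as written and any reuse of it.

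**What to change.** - Apply the no-salvage condition and the treatment-failure rule to overall response and GI response at every time point, in both Parts.
- State that non-responder imputation applies to Day 56 response in Part 2.
- In both duration endpoints, count the start of second-line therapy as the end of response, and exclude first responses that occur after salvage.
- Reconcile Protocol 8.2 and 9.3 with 10.4 on second-line therapy after Day 28, so that it is clear which subjects still have a Day 56 response assessment.

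The cost is definition wording only. All medications are already recorded from consent to completion or termination (Protocol 12.5), so no new data are needed, and the sample size is unchanged. The downside is that later response rates and durations become slightly less favourable.

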8.4.2 Secondary Outcome Measures

8.4.2.1 Efficacy (Parts 1 and 2)

Key Secondary Efficacy Outcome Measures

1. Proportion of subjects achieving GI response at Day 28. Gastrointestinal response is defined as GI CR + PR, which are defined as follows:
 - GI CR is defined as
 - a) Able to eat; not requiring parenteral nutrition, and
 - b) Passing primarily formed stools
 - GI PR is defined as
 - a) Decrease in need for parenteral nutrition to $\leq 50\%$ of required calories; and
 - b) Reduction of stool volume by $\geq 50\%$, without ileus

Other Secondary Efficacy Outcome Measures

1. Proportion of subjects achieving overall response at Day 56
2. Change from baseline in acute GvHD grading at Days 28, 56 and 180
3. Incidence of chronic GvHD at Days 100, 180 and 365

4. Duration of any overall response
5. Duration of any GI response
6. Overall survival through Days 100, 180 and 365
7. Transplant-related mortality at Days 28, 56, 100 and 180
8. Failure-free survival at Days 100 and 180
9. GvHD-free survival at Days 28, 56, 100 and 180
10. Infection-related mortality at Days 28, 56, 100 and 180
11. GvHD-related mortality at Days 28, 56, 100 and 180
12. All-cause mortality at Days 28, 56, 100 and 180

8.4.2.2 Safety Outcome Measures (Parts 1 and 2)

1. The incidence and severity of all AEs, related AEs, all SAEs, related SAEs and temporally-associated AEs
2. Change from baseline in clinical laboratory safety parameters and vital signs
3. Incidence of recurrence of primary malignancies through Days 180 and 365
4. Incidence and type of infection (eg, bacterial, fungal, viral, etc) at Days 28, 56, 180 and 365

8.4.2.3 Pharmacokinetic Outcome Measures (Part 1 Only)

The following noncompartmental analysis PK parameters by day and/or dosing frequency, as applicable, will be assessed:

1. Area under the plasma concentration curve (AUC) from time zero to the last quantifiable activity
2. AUC from time zero to time “t”
3. Systemic clearance at steady state
4. Maximum plasma concentration at steady state
5. AUC from time zero to infinity
6. Apparent volume of distribution at steady state
7. The terminal half-life
8. Mean residence time
9. Trough plasma A₁PI levels at steady state

8.4.3 Exploratory Outcome Measures

Efficacy (Parts 1 and 2)

1. Proportion of subjects achieving GvHD VGPR at Day 28. A GvHD VGPR is defined as follows:
 - Skin: no rash, or residual erythematous rash involving <25% of the body surface, without bullae (residual faint erythema and hyperpigmentation do not count)
 - Liver: total serum bilirubin concentration <2 mg/dL or <25% of baseline at enrollment
 - Gut: tolerating food or enteral feeding, predominantly formed stools, no overt GI bleeding or abdominal cramping and no more than occasional nausea or vomiting
2. Cumulative steroid dose at Days 28, 56, 100 and 180
3. Steroid dose at Days 28, 56 and 100
4. Proportion of subjects achieving GI CR and GI PR at Days 28, 56 and 180 at each baseline GvHD severity grade (B, C and D)

Pharmacokinetics (Parts 1 and 2)

An exploratory, mixed-effects population PK model will be developed from the Part 1 and Part 2 data. Potential exploratory outcome measures include, but are not limited to, the following:

1. Systemic clearance at steady state
2. Maximum plasma concentration at steady state
3. Apparent volume of distribution at steady state
4. The terminal half-life
5. Trough plasma A₁PI levels at steady state

Pharmacodynamics (Parts 1 and 2)

1. Change from baseline in plasma and stool concentrations of A₁PI
2. A₁PI clearance in stool
3. Change from baseline in plasma biomarkers (eg, cytokines IL-2, IL-6, IL-8, and IL-10; and IL-1RA) and stool calprotectin concentrations
4. T cell subpopulations including CD4⁺ CD25⁺ CD127⁺ FoxP3⁺ Tregs

Pharmacodynamics (Part 2 Only)

1. Change from baseline in additional plasma biomarkers on Day 0 and Day 28 (Reg3 α , ST2, and TNFR1)

Health Outcomes (Parts 1 and 2)

1. Change from baseline in QoL as measured by the Functional Assessment of Cancer Therapy-Bone Marrow Transplant subscale version 4.0 instrument (FACT-BMT)
2. Change from baseline in acute GvHD symptoms as measured by the Chronic GvHD Symptom Scale
3. Change from baseline in health utility as measured by European Quality of Life-5 Dimensions-5 Level (EQ-5D-5L)
4. Healthcare resource utilization:
 - Type of admission (hospital, Intensive Care Unit and/or transplant unit)
 - Length of stay
 - Number of unscheduled physician office visits
 - Number of emergency room visits
5. Medication:
 - Days on steroids

8.4.4 Rationale for Endpoints

The primary efficacy endpoint of overall response (GvHD response) was chosen because multiple studies have shown an association between overall response at fixed time points and an improvement in mortality up to 2 years post-transplant.^{21;22;23;24;25;26;27;28} Overall response 28 days after initiating treatment was associated with lower non-relapse mortality at up to 2 years and has been supported as an endpoint in the guidelines issued by an expert panel of the American Society for Blood and Marrow Transplant and results from other studies.^{25;26;27;28}

The key secondary endpoint of GI response was chosen because of the evidence of the role of A₁PI in GvHD with lower GI involvement (Section 6).

The IBMTR Severity Index was chosen to allow comparison with other studies using the IBMTR criteria, including Study FHCRC 2571.

The exploratory endpoint of GvHD VGPR was chosen on the basis of the recommendation of Martin et al.²³ A VGPR approximates a GvHD CR and identifies subjects with excellent responses who may have outcomes similar to subjects with a GvHD CR.

